9.5 Analysis of Secondary Outcomes

9.5.1 PROMIS Pain Interference and Physical Functioning

Secondary analyses will generate point and interval estimates of mean change in the PROMIS physical function and PROMIS pain interference T-scores from baseline to 6 and 12 months between the 2 intervention arms. The 12-month timepoint is primary. These secondary analyses will use appropriate linear mixed model-based approaches analogous to those described for the primary outcome analysis (section 9.3), to take advantage of the data from 6-month assessments for participants who did not complete the 12-month assessment as well as the correlation between the timepoints for participants with both assessments to estimate the change at 12-months for all participants with at least one post-baseline assessment.

Since comparisons at 12 months for these outcomes are two protocol-specified secondary analyses, statistical significance will be assessed with adjustment for multiple comparisons using the Hochberg modification to the Bonferroni adjustment. The Bonferroni adjustment is a simple function of the raw p-values and is computationally

quick but can be too conservative. Step-down methods remove some conservativeness, as do the step-up methods described by Hochberg (1988). The modification procedure rejects all hypotheses with smaller or equal p-values to that of any one found less than its critical value, defined as $(i/m)/Q$ (where I = the individual p-value rank; m = the number of tests; and Q = the false discovery rate). Essentially, if the largest p-value for these two comparisons is < 0.05 , then both tests are considered statistically significant. However, if the largest p-value is > 0.05 then the next largest p-value will be assessed for statistical significance (adjusting for multiple comparison) relative to the number of tests being performed (i.e.: $0.05/2 = 0.025$).

9.6 Analysis of Other Self-Report Outcomes

9.6.1 PROMIS Anxiety, Depression, and Pain Intensity, BPI Pain Interference and Pain Severity

These analyses will generate point and interval estimates of mean change in score from baseline to 6 and 12 months between the 2 intervention arms. These analyses will use appropriate linear mixed model-based approaches analogous to those described for the secondary outcome analysis (section 9.4). Since these outcomes are exploratory in nature, no adjustments for multiple comparisons will be made.

9.6.2 Intent to Taper and Self-Report Opioid Reduction

Self-reported intent to taper opioid medication is collected at baseline, 6 and 12 months, while self-reported opioid reduction since the start of the study is only collected at 6 and 12 months. As mentioned above in section 9.2, for statistical testing, intent to taper will be categorized into a binary measure (Strongly Agree and Agree will be classified as an intent to taper while Uncertain, Disagree, and Strongly Disagree will be classified as no intent to taper). Incidence of intent to taper will be compared between intervention arm using both chi-square test of the original ordinal variable and a logistic generalized mixed model for repeated measures for the dichotomized variable. Self-report opioid reduction will be compared between intervention arm using only a chi-square test of the ordinal variable.

Chi-square tests separately at 6 months and 12 months will stratify by site and will treat the categories as ordinal with no specified numerical spacing between ordered categories using a site-stratified Mantel-Haenszel chi-square test with standardized midrank scores (SAS PROC FREQ scores=modridit option).

For the dichotomous intent to taper outcome, the model will test differences in proportions of the intention to taper opioid use between interventions at 6 and 12 months. The model will include fixed effects for the intervention arm, timepoint, site, intervention-by-time interaction, baseline intent to taper (original 5 levels, treated as a continuous covariate), and baseline opioid MED. The correlation between months 6 and 12 for a participant will be modeled with a Toeplitz structure (i.e. an “RSIDE” random effect) (ref S Davis). Odds ratio and 95% confidence interval for the odds of observing intent to taper will be estimated comparing MI+CBT to SDM).

Statistical analysis modeling will be carried out utilizing SAS/STAT PROC GLIMMIX (SAS Institute Inc. 2017) with the general structure of the SAS code for this model is shown below.

```
Proc glimmix data=Anlydata;
  class patient intervention time site;
  model Taper = intervention time site intervention*time base opioid
  btaper / solution link=logit dist=binary oddsratio DDFM=KR;
  repeated time / type=TOEP subject=patient RSIDE;
  lsmeans intervention*time / ILINK CL; /*estimates event rates*/
  lsmeans intervention*time / oddsratio diff CL; /*estimates Ors*/
  estimate 'MI-CBT vs SDM at 12 Mon' Intervention 1 -1
  intervention*time 0 1 0 -1 / EXP CL;
Run;
```

9.6.3 Discontinuation of Opioid Medications at 12-Months

Opioid discontinuation is an exploratory outcome. Opioid discontinuation at 12 months is identified on the T3 survey with supporting evidence from the prescription record (see definition above in chart). Note the protocol describes an analysis of time to opioid discontinuation, yet this was modified during the analysis planning stage prior to database lock as based on the T3 survey due to complications of not being able to identify absent prescriptions in the electronic record as being due to opioid discontinuation or a participant switching medical care outside the site's health care system.

Contingency table methods will be used to generate point and interval estimates by intervention arm. Treatment groups will be compared using an unadjusted chi-squared test. Event rates are expected to be too small to stratify by clinical site. If event rates are large enough for the risk difference to be relevant, the risk difference 95% CIs will be based on Wald-type CIs under the null hypothesis as specified by Sato. If the expected cell counts < 5, groups will be compared with a Fisher's exact test, and the exact risk difference 95% CI will be obtained using the score statistic based on Chan and Zhang (ref Chan, Zhang 1995). Where specified, Binomial 95% CIs for proportions are based on the exact Clopper-Pearson method (ref Clopper, Pearson).

In SAS, using PROC FREQ:

The chi-square test and corresponding risk difference 95% CI are obtained by:

```
table Intervention*Opid_discont / riskdiff(method=wald equal
  var=null) chisq ;
```

For small expected cell counts, the exact test and risk difference 95% CI are obtained by:

```
table Intervention* Opid_discont / fisher; exact riskdiff
  (method=score);
```

9.6.4 Pre-Specified Subgroup Tests of Heterogeneity and Interaction with Intervention Type on Opioid Use

We will test the interaction of intervention and 2 pre-defined subgroups (having at least one comorbid mental health condition (excluding substance use disorders) and sex) at the $p=0.10$ significance level. Model based analyses to evaluate heterogeneity of intervention effects by the specific subgroups will use a model analogous to those described above for the primary analysis (section 9.3); however, a subgroup type and the interaction between subgroup type and intervention arm will be added to the model. This addition will allow the study team to estimate difference between intervention for each subgroup category separately, and determine if there is a substantial difference in opioid change at 12 months between the subgroups for the SDM and MI+CBT intervention arms (interaction: does one intervention have substantially better or worse outcome than the other intervention for one of the subgroups but not the other subgroup). The general structure of the SAS code is shown below (example is for sex).

```

proc mixed data = INSPIRE_Primanaly method=REML;
  class Unique_ID intervention timepointN Sex clinic;
  model change_OpioidDose_MED = Intervention timepointN clinic
  base opioid intervention*timepointN Sex intervention*Sex
  intervention*Sex*timepointN / s residual DDFM=KR;
  repeated timepointN / type=toep group=intervention
  subject=Unique_ID R RCORR;
  lsmeans Intervention*Sex*timepointN / diff pdiff CL;
  lsmeans intervention*Sex*timepointN "CBT vs. SDM for Females at
  12-months"
    0 0 0 1 0 0 0 0 0 0 0 0
    0 0 0 -1 0 0 0 0 0 0 0 0/ CL;
  lsmeans intervention*Sex*timepointN "CBT vs. SDM for males at
  12-months"
    0 0 0 0 0 0 0 0 0 1 0 0
    0 0 0 0 0 0 0 0 -1 0 0 0/ CL;

  contrast "trt by sex interaction at 12m"
    Intervention*Sex 1 -1 -1 1
    intervention*Sex*timepointN
      0 0 0 1 0 0 0 0 0 -1 0 0
      0 0 0 -1 0 0 0 0 0 1 0 0/ CL;
run;
NOTE: Variable names may differ in the actual data.

```

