Where Y_{ij} is the j th measure of opioid dose in subject i , α is the intercept, β_1 through β_5 are coefficients, and ϵ_{ij} is the residual error term, and the variance-covariance matrix of the residual error terms for an individual is structured with the Toeplitz pattern such that all timepoints have the same variance estimate and all timepoints the same distance apart have the same correlation (i.e., the correlation between months 6 and 9 is assumed to be the same as the correlation between 9 and 12). Note that the protocol specified a random subject effect, but adding a random subject effect does not modify the model or model results in any way and so is excluded.

Statistical analysis modeling will be carried out utilizing SAS/STAT PROC MIXED (Littell, Milliken, Stroup, Wolfinger, & Schabenberger, 2006) with the general structure of the SAS code for this model shown below. Adjusted estimates of the change in opioid dose at each timepoint between the two interventions and corresponding 95% confidence intervals will be produced. The study's primary hypothesis will be tested by estimating the difference in the change in MED between the two intervention arms at 12 months. The study's secondary hypothesis will also be tested and associated effects estimated with the difference in LS means which estimates the average difference in the response outcome between the two intervention arms at each timepoint.

```
proc mixed data = INSPIRE_Primary method=REML;
class Unique_ID Intervention timepointN clinic
model change_OpioidDose_MED = Intervention timepointN clinic baseopioid
intervention*timepointN /s residual DDFM=KR;
repeated timepointN / type=toep group=intervention subject=Unique_ID
R RCORR;
```

```
LSMestimate 'MI-CBT vs SDM at 12 Mon'
  intervention*timepointN 0 0 0  1 0 0
                           0 0 0 -1 0 0 / CL;
  lsmeans intervention*timepointN/ diff pdiff CL;
run;
NOTE: Variable names may differ in the actual data.
```

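### SAP 9.6.4 example code: the male 12-month comparison uses different cell positions in the two arms (10 and 9), and the CLASS order conflicts with the row layout

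*SAP*

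**What the plan says.** SAP 9.6.4 plans to test the interaction of arm with two pre-specified subgroups, comorbid mental health condition and sex, at the 0.10 level. It illustrates the method with code for sex. The relevant parts of that block are:

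- The CLASS line is "class Unique_ID intervention timepointN Sex clinic", so time is listed before sex.
- The three-way effect is written with sex before time. An all-pairs statement on it comes first: "lsmeans Intervention*Sex*timepointN / diff pdiff CL".
- Two labelled comparisons of the arms at 12 months follow, one for females and one for males. Each has one 12-entry row per arm. The female rows have their non-zero entry in position 4 in both arms. The male row for MI+CBT has its 1 in position 10. The male row for SDM is "0 0 0 0 0 0 0 0 -1 0 0 0/ CL", with the −1 in position 9.
- An interaction contrast for 12 months combines "Intervention*Sex 1 -1 -1 1" with two 12-entry rows that use positions 4 and 10 in both arms. The SDM row is "0 0 0 -1 0 0 0 0 0 1 0 0/ CL".

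The text calls the block the general structure of the code, and the note beneath it mentions only variable names. Protocol 5.3.3 commits to model-based treatment effects within the subgroups whether or not the heterogeneity test is significant. SAP 9.6.5 says its ten exploratory covariates will be analysed in the same way as 9.6.4.

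**The concern.** There are two separate faults.

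First, the male comparison picks a different cell in each arm. Both arms share the same sex-by-time layout, so positions 10 and 9 cannot be the same sex at the same month. The interaction contrast in the same block uses position 10 in both arms, so the block also disagrees with itself.

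Second, all six rows are laid out with sex as the outer factor and time as the inner one, while the CLASS line lists time before sex. The documents do not say which order governs the columns. If it is the CLASS order, every row points to the wrong cells.

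What is at stake is the within-sex effect for one of only two pre-specified subgroups, the 0.10-level interaction test, and the use of this block as a template. The mental health subgroup is two-level, as are five of the ten covariates in 9.6.5 (substance use disorder, Charlson none versus any, obesity, non-opioid pain medication, delivery mode). A mislabelled male estimate would look plausible in the output and might not be noticed.

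**Working it through.** **Inputs.** The model has six timepoints (SAP 9.3): months 3, 6, 9, 12, 15 and 18, so month 12 is level t = 4. Sex has two levels. From the labels and signs in 9.6.4, I take females as s = 1, males as s = 2, and MI+CBT as the first arm. Each arm has 2 × 6 = 12 cells, and each of the six printed rows has exactly 12 entries.

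**Position of each cell.**

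- Written order (sex, then time): position = 6(s − 1) + t. Month 12 is at 4 (females) and 6 + 4 = 10 (males).
- CLASS order (time, then sex): position = 2(t − 1) + s. Month 12 is at 2 × 3 + 1 = 7 (females) and 2 × 3 + 2 = 8 (males).

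**What the printed positions select.**

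| Position | Written order | CLASS order |
|---|---|---|
| 4 | females, month 12 | males, month 6 |
| 9 | males, month 9 | females, month 15 |
| 10 | males, month 12 | males, month 15 |

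**What each labelled statement therefore estimates** (F, M = sex; number = month).

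| Label | Written order | CLASS order |
|---|---|---|
| Females, 12 months | CBT F12 − SDM F12 (correct) | CBT M6 − SDM M6 |
| Males, 12 months | CBT M12 − SDM M9 (wrong) | CBT M15 − SDM F15 |
| Interaction, 12 months (three-way rows) | CBT F12 − CBT M12 − SDM F12 + SDM M12 (correct) | CBT M6 − CBT M15 − SDM M6 + SDM M15 |

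**Size of the male error, written order.** Printed minus intended = (CBT M12 − SDM M9) − (CBT M12 − SDM M12) = SDM M12 − SDM M9 = d, the SDM males' mean change between months 9 and 12. The documents give no value for d. For scale only, each 1 MED of d is 1/10 = 10% of the 10 MED difference in Protocol 5.4. If d = 0 there is no numerical error.

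**Estimability of the interaction contrast.** The coefficients on intervention-by-sex must equal the three-way coefficients summed over time.

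- Written order: CBT F = +1, CBT M = −1, SDM F = −1, SDM M = +1. This matches "Intervention*Sex 1 -1 -1 1", and the sums over sex within each arm and month are zero, so the contrast is estimable.
- CLASS order: CBT M = 1 − 1 = 0, SDM M = −1 + 1 = 0, and both female sums are 0. The required two-way line would be 0 0 0 0, but the printed line is 1 −1 −1 1. The required intervention-by-time terms at months 6 and 15 are also absent, so the contrast is not estimable. A check against the full design matrix (rank 24, one per cell) agrees. With the rows rewritten at positions 7 and 8, the contrast becomes estimable and gives the 12-month interaction.

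**Is correcting one coefficient enough?** Moving the SDM −1 to position 10 removes the error in the written order. Under the CLASS order it gives males at month 15 in both arms, so the order must be settled as well.

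**Primary contrast.** SAP 9.3 has "class Unique_ID Intervention timepointN clinic" and an intervention-by-time effect. Both put intervention before time, and the non-zero entry is fourth of six in each arm, so month 12 is selected under either reading.

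**The case against.** The strongest reply is that this is a typing slip in illustrative code that would not produce the analysis. The intent is plain, because the prose and both labels say 12 months. The all-pairs line "lsmeans Intervention*Sex*timepointN / diff pdiff CL" needs no hand-typed coefficients and would print the male and female 12-month arm differences correctly, which meets the protocol's commitment. As printed, the two labelled statements begin with `lsmeans` followed by a label and coefficients, whereas 9.3 uses "LSMestimate 'MI-CBT vs SDM at 12 Mon", so they need rewriting before they yield anything. The CLASS-order consequence depends on a software convention that neither document states. Finally, d is unknown and the subgroup results are hypothesis-generating.

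Much of this stands, and it is why the point is minor. It does not remove it. The 10-versus-9 mismatch needs no software rule. Repairing the keyword alone would leave a statement with the wrong male cell. The correct male difference is one of 24 × 23 / 2 = 276 pairs in the all-pairs output, while the labelled line is the one likely to be read. The SAP gives no other coefficients for these contrasts. The column-order point is conditional, but the disagreement between the CLASS line and the row layout is visible on the page. Under the CLASS order the interaction contrast would give no valid result rather than a silently wrong p-value, so that failure is easier to catch than the male estimate.

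**Conclusion.** The concern holds, as a minor point. At least one labelled statement is wrong as written.

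- If the columns follow the written order, one of the three labelled subgroup statements (the male one) is wrong, by d. The female comparison and the interaction contrast are correct.
- If the columns follow the CLASS line, all three are wrong. The female label carries males at month 6, the male label compares MI+CBT males with SDM females at month 15, and the interaction contrast is not estimable.

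The first fault assumes only that both arms share one sex-by-time layout. Naming the cells also assumes females first, as the labels imply. Loss of an entry when the text was read from PDF is an unlikely explanation, because every row still has 12 entries. The primary analysis in SAP 9.3 is unaffected.

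**What to change.** 1. In the male comparison, move the SDM −1 from position 9 to position 10.
2. List Sex before timepointN in the CLASS line, so that the CLASS order, the written effect and the rows agree. Alternatively, keep the CLASS line and rewrite all six rows with month 12 at positions 7 (females) and 8 (males).
3. Write the two labelled effects as LSMestimate statements, as SAP 9.3 does, with label and effect in the same order in both sections.
4. Add an ESTIMATE of the 12-month interaction beside the contrast.
5. Before use, check each labelled effect against the matching month-12 LSMEANS difference, and check that female minus male equals the added ESTIMATE.

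Do this before the block is reused for the mental health subgroup or the two-level covariates of 9.6.5.

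The cost is one coefficient, one CLASS line, two statement keywords and one added statement (or six rewritten rows), plus an output check. Data, sample size and the primary analysis do not change.

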9.6.5 Exploratory Evaluation of Heterogeneity of Intervention Response to Opioid Use

We will explore treatment heterogeneity for a set of 10 potential covariates listed below, as specified in the protocol and defined in section 9.2 above:

- presence of substance use disorders (yes/no)
- presence of comorbid diseases (Charlson comorbidity index none vs 1 or more),
- Age (< 50, 50-64, 65+),
- baseline pain (BPI pain severity score of mild, moderate, severe),

- health literacy (high, average, and low),
- BMI categories (obese vs. not obese),
- Taking non-opioid pain medications prescribed (yes/no) per T1 survey
- Baseline opioid dose categories (very low, low, moderate, and high).
- Intervention delivery mode (in-person vs. telehealth),
- Number of intervention visits/sessions received: 0, 1-2, 3-4, >4

Testing for heterogeneity of intervention effects for these subgroups will be considered *exploratory*, and the results will be interpreted with appropriate caution. The outcome of interest for these analyses will be change from baseline to 12-months in average prescribed daily opioid dose (in MED). Analyses for these 10 covariates will be conducted the same as for the 2 specified subgroups above (Section 9.6.4), except that p-values will be interpreted descriptively only.

Each covariate will be added individually to a repeated measures MMRM models similar to the primary model described above while intervention arm is still adjusted for in the model .

9.6.6 Percent of Participants Who Experienced an Increase in Pain and Decrease in Opioid Dose

We will explore the percentage of participants per intervention arm who experienced an increase in pain and a decrease in opioid dose. For this analysis, we will create a binary variable for both the PROMIS Pain Interference and Physical Functioning outcomes that identifies participants that experienced an increase in these measures at 12-months since baseline (i.e.: an increase in the Pain Interference T-Score at 12-months and a decrease in the Physical Functioning T-Score at 12-months). We will then categorize their opioid use at 12-months in comparison to baseline as: unchanged (within +/- 10 MED), decreased (<10 MED), or increased (>10 MED).

We will provide descriptive statistics via contingency table that displays the count and proportion of participants, per intervention arm, that experienced an increase in pain but a decrease in opioid prescriptions. No hypothesis or statistical testing will occur.

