3.1.3 Additional Objectives Not Specifically Listed in the Protocol Objectives section

1. Comparison of intervention groups for other self-reported outcomes of anxiety, pain intensity, depression, Brief Pain Inventory (BPI) pain intensity subscale and pain interference subscale, intent to taper, and discontinuation of opioid use.
2. While multiple subgroup analyses have an inherent risk of inflating Type I error, this trial offers a unique opportunity to generate hypotheses about the profile of patients most likely to benefit from the intervention. Consequently, planned *secondary* analyses will assess potential differential treatment effects (treatment by subgroup interaction) for two subgroups: 1) defined by participants with comorbid mental health conditions and 2) sex.
3. The study will also include descriptive *exploratory* analyses to explore the heterogeneity within each intervention arm separately on opioid reduction (predictors of response) according to covariates of interest including age, baseline pain score, comorbidities (including physical comorbidities and mental health disorders, and past or current alcohol or other substance abuse and related disorders), those taking other medications, patient health literacy level, BMI, and opioid dose used at baseline in 3 categories consistent with CDC guidelines: low (20-49 MED), moderate (50-89 MED), high (90 or more MED); we will also have a category for very low (1-19 Med); and intervention delivery mode (in-person vs telehealth). Testing for heterogeneity of treatment effects for these subgroups will be considered exploratory as opposed to confirmatory, and the results will be interpreted with appropriate caution
4. Determine if there is a threshold for the number of completed SDM visits or CBT sessions that results in a clinically significant decrease in opioid use from baseline, defined as a decrease of 10 MED daily dose.

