8. STUDY PARTICIPANT CHARACTERIZATION

8.1 Participant Disposition

Participant eligibility status and disposition will be summarized and described using a standard CONSORT diagram. The diagram will include the number of participants randomized, the

number completing any intervention visits, the number that did not actively withdraw from the study, survey completion rates, and participants with EHR data extraction. Due to the pragmatic nature of the study, many participants may have been marked as completing the intervention phase of the study; however, they did not actually complete any intervention visits and could not be contacted by research coordinators. However, these participants were still included in the study as they received survey invitations and EHR extractions. For CONSORT reporting purposes under the study follow-up section, we will report the number and percentage of those that did NOT actively withdraw or discontinue early and the summary statistics for those that did withdraw or discontinue early. Among those that definitively ended the study early, reasons for study discontinuation or withdrawal will be listed.

In the event a participant is accidentally randomized twice, the participant's first randomization assignment will only be displayed and included in the ITT analyses. The participant's second randomization assignment will be removed from the analysis dataset and subsequent data analyses.

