Substance Use Disorders Flag(s)	Binary	
Includes an indicator for any substance use disorder recorded as a diagnosis in the EHR, as well as binary indicators for the presence in the EHR of each of the following: alcohol use disorder and substance use disorder.
 
The ICD-10 codes used to identify Substance Use Disorders was pulled from the Healthcare Cost and Utilization Project Agency for Healthcare Research and Quality (H-CUP-AHRQ) website (https://hcup-us.ahrq.gov/toolssoftware/ccs10/ccs10.jsp#download)

Age	Continuous and categories	
As reported on the T1 (baseline) survey and captured in REDCap.
 
Age category will also be calculated as:
 
 < 50 50-64 >= 65
Intervention Delivery Mode	Categorical and Binary	
Due to the COVID-19 pandemic, the study began offering telehealth intervention visits beginning in early-May 2020. The intervention visit Case Report Forms (CRFs) were modified to document if a specific intervention visit was administered via telehealth or in-person visit. Since the CRFs were not modified until early-August 2020, all visits up-to-that point will be defined as in-person visits. Descriptive statistics of intervention delivery mode by intervention will be displayed (in-person only, telehealth only, and mixed mode); however, for adjusted analyses, mixed mode will be combined with telehealth to create a binary classification variable.

Variable	Type	Definition
Baseline Opioid MED categories	Ordinal	See the first row in this table regarding the derivation of average daily opioid prescription (in MED). Prescriptions provided 3-months, or 90-days prior to randomization will be considered a participant's baseline opioid MED, classified as None (0 MED), Very low (1-<20 MED) Low (20 - <50 MED), Moderate (50 - <90 MED), and High (90+ MED).
BMI	Continuous and categories	
Derived based on the participant's weight and height obtained from the EHR data (pulled within 90-days of the randomization date).
 
BMI category will also be calculated as:
 
 underweight: <18.5 normal 18.5 - < 25 Overweight 25 - < 30 Obese 30 - <40 Extremely obese >=40 
A dichotomous flag will also be calculated for BMI obese vs not obese.

Sex	Binary	As collected from the T1 (baseline survey); based on birth certificate.

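### SAP 9.6.5 puts delivery mode and sessions received, both determined after randomisation, into the between-arm subgroup model, so the resulting MI+CBT versus SDM differences are not randomised comparisons

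*SAP*

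**What the plan says.** SAP 9.6.4 tests whether the intervention effect differs by sex and by mental-health comorbidity. It takes the primary repeated-measures model, and "a subgroup type and the interaction between subgroup type and intervention arm will be added to the model". The purpose includes being able to "estimate difference between intervention for each subgroup category separately", and the sample code requests the MI+CBT versus SDM contrast at 12 months within each level.

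SAP 9.6.5 then lists ten further covariates and says: "Analyses for these 10 covariates will be conducted the same as for the 2 specified subgroups above", except that p-values are read descriptively. Eight are participant characteristics at entry. The other two are in-person versus telehealth delivery and "Number of intervention visits/sessions received: 0, 1-2, 3-4, >4".

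SAP 9.2 builds both from visits made after assignment. SDM visits count if they fall within the 12-month intervention phase. Delivery mode is in-person only, telehealth only or mixed, with mixed merged into telehealth for modelling. SAP 7.2 nevertheless describes the exploratory work as concerning baseline predictors of response. Protocol 5.3.3 says mode and session count will be explored in a similar way to the other characteristics.

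Objective 4 in SAP 3.1.3 asks whether there is a "threshold for the number of completed SDM visits or CBT sessions that results in a clinically significant decrease in opioid use".

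**The concern.** A subgroup contrast between randomised arms is protected by randomisation when the subgroup is fixed beforehand: within women, for example, the two arms remain exchangeable. That protection is lost when the subgroup is formed by what happened after assignment. Those in Arm 1 who made more than four prescriber visits and those in Arm 2 who attended more than four MI or group sessions were selected by different processes, and nothing balances them.

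The output would be presented as heterogeneity of intervention effect. A reader could conclude that one intervention is better for people who attend often, or when delivered by telehealth, when the pattern may reflect only who attended. Objective 4 adds to this by using a causal verb for an observed visit count.

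**Working it through.** **1. When each variable is fixed.** Sex, age, BMI, literacy, comorbidity, baseline pain and baseline dose are known at or before randomisation. Session count and delivery mode are known only from visits during the following 12 months (SAP 9.2).

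**2. Whether the count means the same in both arms.**
- SDM: 4 to 12 opioid-management visits over about a year (protocol 6.2.1). The same section says patients who taper may be seen more often. SAP 5.2 expects many SDM participants to have only three visits if prescriptions can be renewed without one. The count therefore partly tracks prescribing, which is the outcome.
- MI+CBT: one MI session and up to eight group sessions, anticipated within about three months of enrolment though possibly longer (protocol 6.3.1). The documents describe no corresponding link between tapering and the number of sessions.
- Timing: the 12-month outcome is the average dose over months 9 to 12 (SAP 9.3), while SDM visits are counted up to month 12. Exposure and outcome windows overlap.

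**3. Whether mode is free of the count.** Mixed is merged with telehealth, so telehealth means at least one telehealth visit and becomes likelier as visits accumulate. If each visit independently had a 50% chance of being telehealth (an assumption), the in-person share would be 0.5 after one visit and 0.5^4 = 0.06 after four.

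**4. Zero visits.** SAP 8.1 allows that many participants may be marked as completing the intervention phase although "they did not actually complete any intervention visits and could not be contacted by research coordinators". They have a level in the session variable (0) but none in the mode variable. A mixed model omits records with a missing class variable, so they would probably leave the mode analysis. The SAP gives no rule.

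**5. Illustration of the mechanism for session count.** The plan's own figure is reproduced first. For a 10 MED difference, SD 40, two-sided 0.05 and 80% power, the normal approximation gives 2 × (1.960 + 0.842)² × 40²/10² = 251.2, so 252 per arm. The t-based calculation gives 252.1, so 253 per arm and 506 in total, as stated in SAP section 6. That figure is not in dispute; it supplies the SD.

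Document inputs: 526 randomised, 12% missing (526 × 0.88 / 2 ≈ 231 per arm), SD 40. Assumed inputs: no arm effect, no effect of sessions on dose, attendance of 15/25/25/35% across the four categories in both arms, and correlation ρ between visit count and dose reduction in SDM only.

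With a normal latent attendance score, the mean change in an SDM end stratum holding share p differs from the arm mean by ρ × 40 × φ(z_p)/p in absolute value.
- Zero visits, p = 0.15: φ/p = 0.2332/0.15 = 1.554. For ρ = 0.1, 0.2, 0.3 the shift is 6.2, 12.4, 18.7 MED.
- More than four, p = 0.35: φ/p = 0.3704/0.35 = 1.058. The shift is 4.2, 8.5, 12.7 MED.

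The simulation (4,000 trials per setting) agrees:

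| ρ in SDM only | MI+CBT minus SDM, 0 visits | MI+CBT minus SDM, >4 visits | Interaction p < 0.10 |
|---|---|---|---|
| 0.1 | −6.0 | +4.3 | 19% |
| 0.2 | −12.5 | +8.5 | 47% |
| 0.3 | −18.7 | +12.7 | 81% |

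The true difference is zero in every cell, and 10% of interaction tests should fall below 0.10. With ρ = 0.3 in both arms but different attendance (SDM 10/30/30/30%, MI+CBT 30/15/15/40%), the stratum differences run from −7.3 to +2.3 MED and 20% fall below 0.10. With the same ρ and the same attendance in both arms, the differences are about zero and about 10% fall below 0.10.

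**The case against.** The strongest defence is that these analyses are already downgraded: 9.6.5 is titled exploratory, its p-values are descriptive, and caution is promised. This limits the weight of the point. It does not remove selection from the point estimates, which would still be reported as effects by stratum.

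A second defence is that the SAP may intend something milder. Objective 3.1.3(3) speaks of heterogeneity within each arm separately and includes delivery mode, though not session count. The last sentence of 9.6.5 could describe a model merely adjusted for arm. But 9.6.5 also says explicitly that the method is the same as in 9.6.4, which is between-arm. The SAP is inconsistent, and the within-arm reading is the one to keep.

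Third, part of delivery mode follows calendar time, which randomisation balances. The rest depends on the patient, the arm and the number of visits.

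Several stronger readings are tempting but not supported:
- **That non-attenders certainly and silently vanish.** The handling is not stated. They stay in the session analysis, and the CONSORT diagram reports how many completed any visit.
- **That their loss from the mode analysis biases the result by some given number of MED.** The documents give neither non-attendance by arm nor the outcome difference. A shift common to both modes cancels from the arm-by-mode interaction, and equal non-attendance related to outcome in the same way gives no shift.
- **That the 3-4 band defeats objective 4.** SAP 9.2 also keeps sessions as a count, and nothing ties that objective to 9.6.5.
- **That randomisation before or after telehealth began could stand in for mode received.** SAP 9.2 says "the study began offering telehealth intervention visits beginning in early-May 2020". With enrolment expected from April 2019 and a 12-month intervention, people randomised from about May 2019 to April 2020 would count as before, yet had telehealth available for part of their course.

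**Conclusion.** The point holds for the two post-randomisation covariates in SAP 9.6.5. Their stratum-specific MI+CBT versus SDM differences are not randomised comparisons and should not be labelled heterogeneity of intervention effect. For session count, the protocol itself supplies a route from outcome to exposure in one arm only.

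The size of the bias cannot be given from the documents. The figures above rest on assumed correlations and attendance shares and show only that an apparent difference larger than 10 MED can arise with no true effect. Bias is absent in the illustration when attendance relates to outcome in the same way and at the same rates in both arms, which the documents give no reason to expect. Loss of zero-visit participants from the mode model is a probable consequence, not a stated one.

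The primary test and the two key secondary tests are unaffected, and so are the other eight covariates. The matter is worth correcting before reporting but does not threaten the trial's main conclusion.

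**What to change.** 1. Remove delivery mode and session count from the between-arm interaction models in SAP 9.6.5, leaving eight covariates there.
2. Report change in MED by session count and by delivery mode within each arm only, labelled as non-randomised association. This agrees with the within-arm wording of objective 3.1.3(3).
3. Show participants with no visits as their own category in the mode table.
4. Record this as a departure from protocol 5.3.3. The SAP already records others, such as the changed discontinuation outcome in 9.6.3.
5. In objective 3.1.3(4), replace *results in* with *is associated with*.

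The cost is SAP wording and a noted protocol departure, with no new data. The downside is that there will be no between-arm estimate by mode or session count.
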